17.3 Study eQuestionnaires

Subjects will be provided with two types of electronic questionnaires throughout the course of this study:

- **Subject eDiary** will be distributed to all subjects for the collection of safety information from the day of vaccination until the first 10 post-vaccination days (i.e. including the day of vaccination)
- **eMemory Aid** will be distributed to all subjects for the collection of safety information outside the first 10 post-vaccination days until the next Visit .

The following information will be collected in the Subject eDiary (10 days post-vaccination):

- Measurement of oral body temperature (For further information see Section 17.2.2.3);

- Solicited injection site reactions ^{xii} (injection site pain, tenderness, redness, induration and swelling), for further information see Section 17.2.2.1;
- Solicited systemic reactions ^{xii} (fever, fatigue, headache, nausea/vomiting, muscle pain, joint pain, rash);
- Other AEs;
- Any new concomitant medication or changes in medication taken after vaccination;
- Information on travel to geographical regions where CHIKV is endemic.

The following information will be collected in the eMemory Aid (outside 10 day post-vaccination period):

- AEs;
- Any new concomitant medication or changes in medication taken after vaccination;
- Ongoing solicited reactions;
- Information on travel to geographical regions where CHIKV is endemic.

Assessments by the subject should occur at the same time each day, starting approximately 8 hours after vaccination. The subject will be properly instructed on the reporting requirements and how to complete and use the subject diaries, thermometer and measuring device (for assessment of measurable injection site reactions).

Questionnaires are always to be assessed at the next visit by the Investigator together with the subject, prior to these data being entered into the electronic case report form (eCRF). The Investigator will review and discuss the questionnaires with the subject, ask about AEs occurring since the last visit and ensures completeness and reliability of self-reporting. The entries in the respective questionnaires shall be evaluated and graded for severity and relatedness to the vaccination by the Investigator.

The eQuestionnaires will serve as source documentation. Entries in the eQuestionnaires will be transcribed into the appropriate eCRFs. Any entry on the eCRF that does not correspond with an entry in the eDiary will be explained by the Investigator on the relevant questionnaire page.

17.4 Medical, Medication, and Non-Drug Therapy History

17.4.1 Medical history

At screening, the subject's medical history will be described for the following body systems including severity (mild, moderate, or severe as defined in Section 17.2.1.1) or surgery and

^{xii} Solicited injection site and systemic reactions in the Subject eDiary will be assessed by the subject for absence, presence and duration.

start and end dates, if known: eyes, ears, nose, and throat; respiratory; cardiovascular; gastrointestinal; musculoskeletal; neurological; endocrine; metabolic; hematopoietic/lymphatic; dermatological; and genitourinary.

In addition, the medical history covering the last 3 years prior to screening will include the following:

- Information on prior vaccination against relevant traveler diseases (i.e. yellow fever, Japanese encephalitis)
- Previous chikungunya virus infection;
- Other vector-borne diseases in the past;
- Previous trauma to joints;
- Information on planned hospitalizations (including elective surgery) during the study for medical conditions existing prior to or at study entry. Such planned hospitalizations will not need to be reported as SAEs.

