12. STUDY DESIGN

12.1 Overall Study Design

This is a prospective, randomized, double-blinded, multicenter Phase 3 clinical study investigating three Lots of VLA1553 at the final dose (target 1x 10E4 TCID₅₀ per 0.5 mL). Overall, approximately 402 subjects will be enrolled (i.e. ICF signed) into the study, approximately 134 subjects per VLA1553 Lot (**Table 3**).

Subjects will be block-randomized in a 1:1:1 ratio into the three study arms to receive either of three Lots of VLA1553 as a single i.m. vaccination on Day 1 (Visit 1).

All subjects will be asked to return to the study site at Day 8 (Visit 2), Day 29 (Visit 3), Day 85 (Visit 4) and Month 6 (Day 180, Visit 5) for immunogenicity sampling. Safety data collection will capture solicited AEs until Day 11 and unsolicited AEs up to Day 180 (Month 6, Visit 5) from all subjects. AESIs will be captured 2 to 21 days post-vaccination. Subjects presenting with acute arthralgia within this time period will be followed-up until resolution and monitored for recurrences until the end of the study. SAEs will also be assessed until the end of the study (Month 6, Visit 5).

Table 2 below illustrates the subject distribution scheme.

Table 3. Subject Distribution

Study Arms	Vaccine	Cohort	Number of subjects (n)	Target Dose (TCID ₅₀ /dose)	Injection Volume (mL)
1	VLA1553	Lot 1	134	1x 10E4 TCID ₅₀ per 0.5 mL	0.5
2	VLA1553	Lot 2	134		0.5
3	VLA1553	Lot 3	134		0.5
Total N:					402

The clinical study design is displayed in the **Figure 1** below.

[figure not shown]

Figure 1. Study Design Lot-to-Lot Consistency Study VLA1553-302

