12.3.2 Secondary Endpoints

Immunogenicity

The following secondary immunogenicity endpoints will be evaluated:

- Immune response as measured by CHIKV-specific neutralizing antibody titers on Day 8, Day 85 and Month 6 post-vaccination as determined by μ PRNT assay;
- Proportion of subjects with seroprotective levels (defined as [REDACTED] for baseline negative subjects) at Days 8, 29, 85 and Month 6 post-vaccination by μ PRNT assay;
- Proportion of subjects with seroconversion at Day 29 and Month 6 as determined by μ PRNT assay (seroconversion defined as CHIKV-specific neutralizing antibody titer of [REDACTED] for baseline negative subjects and [REDACTED] for baseline positive subjects);
- Fold increase of CHIKV-specific neutralizing antibody titers determined by μ PRNT assay at Days 8, 29, 85 and Month 6 post-vaccination as compared to baseline;
- Proportion of subjects reaching an at least 4-fold, 8-fold, 16-fold or 64-fold increase in CHIKV-specific neutralizing antibody titer compared to baseline as measured by μ PRNT assay.

Safety:

- Frequency and severity of solicited injection site and systemic reactions within 10 days post-vaccination;
- Frequency and severity of unsolicited adverse events (AEs) within 28 days post-vaccination;
- Frequency and severity of any AE during the entire study period;
- Frequency and severity of any serious adverse event (SAE) during the entire study period;
- Frequency and severity of any adverse event of special interest (AESI) within 2 to 21 days post-vaccination.

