15.4.1 Part A

Table 15.4-1
Study VLA1553-302 Study Visit Schedule – Part A

VISIT	TIME	ACTION
Visit 0 Screening	Day -28 to 0 (prior to Visit 1)	
 1. Informed consent ^a 2. Inclusion and exclusion criteria (Section 13.1 and 13.2) 3. Demographics ^b 4. Medical history including vaccination history ^c (Section 17.4.1) 5. Prior and concomitant Medications (Section 17.4.2) 6. Physical examination, Hand Stiffness Test ^d and Vital Signs ^e (Section 17.6 and 17.5) 7. Blood draw and urine sample for: 
 a) Serum Pregnancy test ^f b) CHIK Screening ^g c) Safety Sample ^h d) HIV / HBsAg / HCV testing ⁱ
Visit 1 ^j	Day 1	
 1. Inclusion, exclusion and delay criteria (review) (Section 13.1, 13.2 and 13.3) 2. Medical History incl. vaccination history ^c (update) (Section 17.4.1) 3. Concomitant Medications (Section 17.4.2) 4. Symptom-driven physical examination, Hand Stiffness Test ^d and Vital Signs ^e (Section 17.6 and 17.5) 5. Blood draw and urine sample for: 
 a) Urine Pregnancy test ^f b) Baseline Sample ^j c) Immunogenicity ^k d) Viremia ^l e) Safety Sample ^h f) COVID-19 Sample ⁿ 6. Randomization (Section 12.4) 7. VACCINATION (Section 15.3.2)

Table 15.4-1
Study VLA1553-302 Study Visit Schedule – Part A

VISIT	TIME	ACTION
		8. Post-vaccination observation (Section 15.3.3) 9. AE documentation (Section 17.2) 10. Instruct on Subject eDiary ^m (Section 17.3)
Visit 2	Day 8 (+/- 1d)	1. Review Subject eDiary (Section 17.3) 2. AE documentation (Section 17.2) 3. Concomitant medications (17.4.2) 4. Symptom-driven physical examination and Hand Stiffness Test ^d (Section 17.6) 5. Blood draw and urine sample for: a) Immunogenicity ^k b) Viremia ^l c) Safety Sample ^h 6. Instruct on eMemory Aid (Section 17.3)
Visit 3	Day 29 Month 1 (+/- 4d)	1. Review eDiary and eMemory Aid (Section 17.3) 2. AE documentation (Section 17.2) 3. Concomitant Medications (Section 17.4.2) 4. Symptom-driven physical examination and Hand Stiffness Test ^d (Section 17.6) 5. Blood draw and urine sample for: a) Urine Pregnancy test ^f b) Immunogenicity ^k c) Viremia ^l g) Safety Sample ^h h) COVID-19 Sample ⁿ

^a Occurs at enrollment (before Screening).
^b Demographics data include year of birth, age, height, weight, BMI, gender, race and ethnicity.

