15.5 Procedures for Monitoring Subject Compliance

All study procedures are to be performed under the supervision of the Investigator at the study site, and thus, no separate procedures will be used to monitor subject compliance.

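### For symptom-based solicited reactions the protocol lists no same-day severity item, so grades for onsets after Visit 2 may rest on about three weeks' recall

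*Protocol*

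**What the plan says.** Protocol 12.3.2 lists as a secondary safety endpoint "Frequency and severity of solicited injection site and systemic reactions within 10 days post-vaccination". SAP 9.3 repeats it, and SAP 13.5.1 tabulates these events by preferred term and severity and adds radar plots of maximum severity.

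Footnote xii, attached to both solicited items in Protocol 17.3 and printed on the page of 17.4.1, limits what the subject assesses: "Solicited injection site and systemic reactions in the Subject eDiary will be assessed by the subject for absence, presence and duration". Section 17.3 then says "The entries in the respective questionnaires shall be evaluated and graded for severity and relatedness to the vaccination by the Investigator", and on timing "Questionnaires are always to be assessed at the next visit by the Investigator together with the subject".

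The eDiary also takes oral temperatures with date and time (17.2.2.3), the longest diameter of measurable injection site reactions (17.2.2.1), and new or changed medication (17.3).

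On the calendar, Protocol 12.1 says "Safety data collection will capture solicited AEs until Day 11". Table 15.4-1 puts Visit 2 at Day 8 with one day either side. The next visit is "Day 29 Month 1 (+/- 4d)", where the listed action is "Review eDiary and eMemory Aid (Section 17.3)".

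Protocol 15.5 reasons that all procedures are supervised at the site, and so "no separate procedures will be used to monitor subject compliance".

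**The concern.** Tables 17.2-1 and 17.2-2 grade most reactions by their effect on a given day: how far activity was disturbed, what kind of discomfort there was, how many episodes occurred in 24 hours, how much skin was involved. These are facts of the day, and for most reactions the listed diary content does not hold them. The investigator has to reconstruct them with the subject at the next visit. For anything that begins or worsens after Visit 2, that visit is about three weeks away.

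At stake is the Grade 1 versus Grade 2 split for the common systemic symptoms. Protocol 10.4 gives expansion of the safety database at the final dose as an aim of the study, so the absolute severity profile matters in its own right. The eQuestionnaires are the source documents (17.3). As listed, they hold nothing against which such a grade could be verified, and severity not captured on the day cannot be recovered later.

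**Working it through.** The documents state no figure for this delay, so there is none to reproduce. The check has two parts.

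**1. Which graded rows have a same-day record?** Table 17.2-1 has 4 rows and Table 17.2-2 has 7, so 4 + 7 = 11.

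| Row | Basis of grade below Grade 4 | Listed same-day eDiary item |
|---|---|---|
| Fever | temperature | yes |
| Redness | diameter | yes |
| Induration/swelling | diameter and activity | diameter only |
| Injection site pain | analgesic use or activity | medication only |
| Headache | analgesic use or activity | medication only |
| Tenderness | type of discomfort | none |
| Nausea/vomiting | activity, episode count or IV hydration | none |
| Fatigue | activity | none |
| Myalgia | activity | none |
| Arthralgia | activity | none |
| Rash | body surface area and daily living | none |

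Covered: 2. Partly covered: 3. No listed item: 6. Check: 2 + 3 + 6 = 11.

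**2. How long from onset to routine grading?** Delay = day of next visit − day of onset.

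Inputs: Visit 2 on Days 7 to 9 and Visit 3 on Days 25 to 33 (Table 15.4-1). The solicited period ends on Day 11 (12.1), or on Day 10 if the vaccination day counts as one of the ten days (17.2.2.3 and 17.3 can be read that way).

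- Onset before Visit 2: at most 9 − 1 = 8 days.
- Onset after Visit 2, nominal visits: 29 − 8 = 21 days (onset later on the day of Visit 2) down to 29 − 11 = 18 days (19 if the period ends on Day 10).
- Shortest at the window limits: 25 − 11 = 14 days (25 − 10 = 15 if the period ends on Day 10).
- Longest at the window limits: 33 − 7 = 26 days, with Visit 2 on Day 7, onset later that day and Visit 3 on Day 33 (25 if onset is the next day).
- Diary days after a Day 8 visit: Days 9 to 11, so 3 of 11 (2 of 10 if the period ends on Day 10).

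Counting onsets understates the exposure a little. The recorded grade is the highest reached during the event (Protocol 17.2.1.3, SAP 11.7.1), so a reaction that starts before Visit 2 and worsens afterwards also depends on the Visit 3 review.

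**Does the SAP repair this?** SAP 11.7.6 flags as recall events those solicited AEs that are on the CRF but not in the eDiary, and SAP 13.5.1 has a table without them. The flag concerns whether a reaction was entered. A reaction entered in the diary but graded three weeks later passes unflagged.

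**The case against.** The strongest reply is that investigator grading is a legitimate choice and is not unstructured here. It uses fixed criteria, takes place with the subject over a dated diary, and 17.3 requires the investigator to check completeness and reliability and to explain mismatches between diary and eCRF. All of that stands. It does not supply the missing daily fact on which the grade turns.

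Several stronger readings are tempting, and the documents do not support them:

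- *That the diary holds nothing but presence and duration.* It also takes temperature, lesion diameter and medication, so fever and redness are covered and pain, headache and induration/swelling are partly covered.
- *That 26 days is the usual lag.* It needs both visits at opposite window limits and onset on the day of an early Visit 2.
- *That Grade 3 reactions reach the DSMB late or downgraded.* Subjects are told to inform the site immediately of severe solicited reactions (Table 15.4-1, note m), unscheduled visits are available (15.4.3), and the sponsor reviews blinded listings until the last subject reaches Day 29 (17.11.2). Recall error could go in either direction.
- *That the lot comparison is biased.* All three lots share one blinded schedule, and nothing suggests that recall differs by lot.

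Two further objections carry weight. The eDiary screens are not in the documents, so a severity prompt may already exist; if so, footnote xii is wrong and needs correcting. And asking lay subjects to judge rash by body surface area would be unsound, so that should stay with the investigator.

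**Conclusion.** The point holds as a cheap improvement to a stated secondary endpoint. For 6 of 11 graded rows, and for the activity part of 3 more, the protocol lists no same-day eDiary item that matches its own grading criteria. For onsets or worsening after Visit 2, the grade, chiefly mild versus moderate, may rest on recall of typically 18 to 21 days, with limits of 14 and 26 days. The consequence is a less reliable absolute severity profile. The primary immunogenicity analysis is untouched, and no distortion between lots is shown.

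This assumes that footnote xii and the lists in 17.3 describe the eDiary as built, and that no unscheduled contact brings the grading forward. The documents give no distribution of onset days, so the share of reactions affected cannot be estimated.

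The rationale in 15.5 is a smaller, related fault: solicited reactions, diameters and temperatures are recorded by the subject away from the site, so supervision at the site does not cover them.

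**What to change.** 1. In Protocol 17.3 and footnote xii, have the subject enter, for each reaction present on each diary day, the functional level in the terms of Tables 17.2-1 and 17.2-2: effect on activity, discomfort, episodes per 24 hours. State there that temperature, diameter and medication are also recorded.
2. Leave the final grade with the investigator, who explains any departure from the maximum daily level and assesses the extent of rash.
3. Add an automatic eDiary completion check during the diary period, and a remote site review when the diary closes instead of waiting for Visit 3.
4. Correct the rationale in 15.5 to acknowledge data recorded away from the site.
5. State whether the solicited period ends on Day 10 or Day 11, so that diary close is unambiguous.

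The cost is one extra response per reaction per day, an eDiary reconfiguration and a protocol amendment needing IRB approval (19.2). Section 13.3 shows that subjects were already screened under version 2.0, so the change may come after enrolment has started. In that case, record which subjects used which diary version, because two ways of collecting severity would otherwise be mixed within one endpoint.

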17.4.2 Concomitant Medications and Non-Drug Therapies

All medications (including vaccinations) received from 2 weeks prior to study enrollment until completion/termination should be collected from all subjects, and recorded on the appropriate eCRF. In addition to product name (generic name), the dose, indication, route of administration and frequency as well as the start and end date of treatment will be documented.

In addition, medications to treat SAEs will be reported to the Sponsor on SAE Report Forms as described in Section 3. In context of this study, information on non-drug therapies will only be collected in relation to SAEs.

The following medications are **not permitted** if administered within the specified study periods (unless such treatment has to be administered in an emergency situation):

- Any blood products or immunoglobulins during the course of the study;
- Immunosuppressive therapies (e.g. systemic or high dose inhaled [>800 µg/day of beclomethasone dipropionate or equivalent] corticosteroids, radiation treatment or other immunosuppressive or cytotoxic drugs) during the course of the study;
- Prophylactic administration of antipyretics within 4 hours prior to and during the first 72 hours after vaccination;
- Subjects are requested to refrain from donation of blood, blood fractions and plasma within 30 days prior to vaccination and for the entire study duration

For documentary purposes, any of the treatments listed above (including emergency treatment) given within these time periods requires special documentation and is to be documented as a protocol deviation.

The following medications and procedures will **delay** vaccination:

- antipyretics received within 4 hours prior to vaccination.
- any live or inactivated vaccine received within 28 days or 14 days prior to vaccination, respectively.

Usage of any other medications or non-drug therapies is not restricted.

Additionally, medications that are not permitted prior to study enrollment, resulting in exclusion from the study, are reflected in the exclusion criteria in Section 13.2.

17.5 Vital Signs

Vital signs will include body temperature (°C / °F) measured orally, pulse rate (beats/min), and systolic and diastolic blood pressure (mmHg) while seated and at rest.

Vital signs will be measured at screening (Visit 0) and at the vaccination visit (Visit 1) and are to be recorded before the vaccination is given. In addition, after an observation period of 30 minutes at the study site following vaccination pulse rate as well as blood pressure while seated and at rest will again be assessed.

Vital sign values are to be recorded on the appropriate eCRF. For each vital sign value, the Investigator will determine whether the value is considered an AE (see definition in Section 17.1.1). If assessed as an AE, the medical diagnosis (preferably), symptom, or sign, will be recorded on the AE eCRF. Additional tests and other evaluations required to establish the significance or etiology of an abnormal result, or to monitor the course of an AE should be obtained when clinically indicated. Any abnormal value that persists should be followed at the discretion of the Investigator.

17.6 Physical Examinations

At screening (Visit 0), a physical examination will be performed on the following body systems being described as **normal** or **abnormal**: general appearance, head and neck, eyes and ears, nose and throat, chest, lungs, heart, abdomen, extremities and joints, lymph nodes, skin, and neurological.

A symptom-driven physical examination will be performed at all study Visits except the Screening Visit (Visit 0), i.e. only in case a symptom is reported by the subject, a system-based assessment will be performed for a detailed check of the affected body system(s). A symptom-driven examination should also be performed in case the subject has complaints within the observation time after vaccination (as described in 24.2, Visit 0 Screening).

A Hand Stiffness examination will be performed at all study Visits irrespective of any clinical signs or symptoms. The subject will be asked to bend simultaneously the four fingers of both hands, i.e. index, middle, ring, and little finger and the range of motion will be measured with a measuring device. Specifically, the distance between the fingers and

the ball of the thumb should be measured in cm or inch. The distance of the least flexible finger of each hand should be measured and recorded in the eCRF. Importantly, the same finger of each hand should be measured for subsequent visits. Special attention should be paid to measuring consistently to the same part of the ball of the thumb.

Abnormal conditions detected at screening or prior to vaccination at Visit 1 will be recorded as medical history. At all other study visits, if a new abnormal or worsened abnormal pre-existing condition is detected, the condition will be recorded as an AE. A guidance document on the hand stiffness test is included in the Supplement Section (see Section 24.4).

17.7 Clinical Laboratory Parameters

Blood and urine samples will be obtained for assessment of clinical laboratory parameters as outlined in the Schedule of Study Procedures (see Section 24.2) or in the Screening and Study Visits Section (see Section 15.4). Parameters will be analyzed by central laboratories according to the applicable laboratory SOP.

17.7.1 Safety Sample

A (baseline) safety laboratory blood [13.0 mL] and urine sample will be obtained at Visit 0 (Screening Visit) and all subsequent visits from all subjects for standard clinical chemistry, hematology, coagulation panel and urinalysis as well as for HIV / HBsAg / HCV [5.0 mL] testing (at the Screening Visit only).

Clinical chemistry (approx. 3.5 mL)	Creatinine, sodium, potassium, calcium, aspartate transaminase (AST), alanine aminotransferase (ALT), alkaline phosphatase, bilirubin and C-reactive protein (CRP).
Hematology panel (approx. 5.0 mL)	Hemoglobin, hematocrit, erythrocyte count, WBC count, differential WBC count (basophils, eosinophils, lymphocytes, monocytes, neutrophils), platelets, ESR.
Coagulation panel (approx. 4.5 mL)	Small blood coagulation (prothrombin time, aPTT and fibrinogen).
HBsAg/ HCV / HIV test (approx. 5.0 mL)	A positive HIV test obtained by ELISA will have to be confirmed by a second method [e.g. Western blotting or PCR], at Visit 0 only.
Urinalysis	Standard urine dipstick for determining pH-value, specific gravity, leucocytes, nitrite, protein, glucose, ketones, urobilinogen, bilirubin, erythrocytes.

